### **2.3.2 Known Potential Benefits**

The completed Phase 1 study in normal healthy volunteers was designed primarily to evaluate safety and local tolerability, with efficacy collected as an exploratory endpoint. Preliminary evidence of PD activity as measured by gene expression changes and a reduction of fibroplasia following MRG-201 treatment has been observed and warrants further investigation.

### **3 STUDY OBJECTIVES AND ENDPOINTS**

#### **3.1 Objectives**

##### **3.1.1 Safety Objective**

Investigate the safety and tolerability of multiple intradermal administrations of MRG-201 in subjects with a history of keloids.

##### **3.1.2 Pharmacodynamic Objective**

Investigate the activity of MRG-201 in prevention or reduction of keloid formation, in subjects with a history of keloids.

##### **3.1.3 Other Objectives**

- Evaluate additional pharmacodynamic endpoints of MRG-201 in subjects with a history of keloids.
- Evaluate Patient Reported Outcomes.
- Characterize the pharmacokinetics of MRG-201 in subjects with a history of keloids.

### **3.2 Endpoints**

#### **3.2.1 Safety Endpoints**

- The safety and tolerability of MRG-201 will be assessed by determining the incidence and severity of clinically significant adverse events (including Grade 3 and 4 AEs, treatment-related AEs, SAEs, and AEs requiring discontinuation of MRG-201), and physical examination findings, changes in vital signs, electrocardiograms (ECGs), and laboratory parameters.
- AEs will be assessed according to the National Cancer Institute (NCI) Common Terminology Criteria for Adverse Events (CTCAE), version 5.0.

#### **3.2.2 Pharmacodynamic Endpoint**

The formation of a keloid will be defined as a persistent scar that exhibits a score of at least 3 on the mVSS ([Fearmonti et al 2010](#), see [Appendix D](#)), with a score of at least 1 in the height sub-domain. For the purposes of this study, scars that form at one or both of the blinded wound sites following the initial treatment will be considered unconfirmed keloid(s) if they exhibit a

score of 3 to 5 on the mVSS, with a score of at least 1 in the height sub-domain. Unconfirmed keloid(s) with a score of 3 to 5 on the mVSS will be re-evaluated at the subsequent monthly visits for up to 12 weeks. Keloid(s) that persist after this 12-week observation period and/or progress to an mVSS score of  $\geq 6$  at any time (with a score of at least 1 in the height sub-domain) will be considered confirmed keloid(s). At the time of keloid confirmation, the investigator, in consultation with the subject, may elect to attempt local treatment of the keloid with triamcinolone as a standard of care therapy after consultation with the sponsor.

- Proportion of confirmed keloid formation at 24 weeks across subjects for treated vs. untreated lesions.
- Proportion of subjects with improvement, which is defined as no confirmed keloid formation in the treated lesion vs. confirmed keloid formation in the untreated lesion.
- Proportion of subjects forming confirmed keloids with MRG-201 treatment vs. placebo treatment at 12 weeks, 36 weeks, 52 weeks, and at the time of study withdrawal (if subjects do not complete the study).

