For subjects receiving 6 doses of MRG-201 in the initial treatment cycle, if there is evidence that a keloid may be forming (defined as meeting a score of 1 or 2 on the mVSS and having an appearance consistent with an area likely to form a keloid according to investigator judgement) within 12 weeks after initiation of the first cycle of study dosing, and following the initial 29-day treatment and assessment period, subjects will undergo a second cycle of study dosing in one or both biopsy sites (depending on keloid formation). Subjects will be treated with MRG-201 or placebo according to the original treatment assignments (blinding will be maintained during the second treatment regimen). The treatment regimen for the second cycle of study dosing will be the same as for the first cycle, i.e., an initial dose followed by additional doses 2, 4, 7, 9, and 11 days after the initial dose, with follow-up visits at Days 19 and 29 after the re-start of dosing. Following the visit that occurs 29 days after the start of the second cycle of study dosing, re-treated biopsy sites will be followed according to the first cycle visit schedule. If the wound site scar(s) progress to an mVSS score of 3 to 5 (with a score of at least 1 in the height sub-domain) after the 12-week observation period and/or to an mVSS score of  $\geq 6$  at any time (with a score of at least 1 in the height sub-domain), the scar(s) will be considered confirmed keloid(s). At the time of keloid confirmation, the investigator, in consultation with the subject, may elect to attempt local treatment of the keloid with triamcinolone as a standard of care therapy after consultation with the sponsor.

Additional cohorts may be enrolled to test lower doses or an extended dosing schedule. Study procedures for the extended dosing cohorts will be identical to the cohort described above, with the following exceptions: 1) subjects in these cohorts may receive a total of 12 intradermal doses of MRG-201 and placebo on Days 1, 3, 5, 8, 10, 12, 15, 17, 19, 22, 24, and 26; 2) subjects will not undergo a second cycle of treatment if the 4-week dosing schedule is used; and 3) pharmacokinetic assessments will be performed on study Day 1, 2, 26, and 27 for subjects receiving an initial 26-day treatment cycle.

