**Figure 2: Pictorial Guide to Punch Biopsy Locations**

#### 7.4.2 Physician Assessment of Keloid Formation

Excisional wound sites will be evaluated by the investigator for keloid formation (predose on dosing days) at the time points outlined in [Appendix A](#) and [Appendix B](#), utilizing the mVSS and POSAS scales.

The formation of a keloid will be defined as a persistent scar that exhibits a score of at least 3 on the mVSS ([Fearmonti et al 2010](#), see [Appendix D](#)), with a score of at least 1 in the height sub-domain. For the purposes of this study, scars that form at one or both of the blinded wound sites following the initial treatment will be considered unconfirmed keloid(s) if they exhibit a score of 3 to 5 on the mVSS, with a score of at least 1 in the height sub-domain. Unconfirmed keloid(s) with a score of 3 to 5 on the mVSS will be re-evaluated at the subsequent monthly

visits for up to 12 weeks. Keloid(s) that persist after this 12-week observation period and/or progress to an mVSS score of  $\geq 6$  at any time (with a score of at least 1 in the height sub-domain) will be considered confirmed keloid(s). At the time of keloid confirmation, the investigator, in consultation with the subject, may elect to attempt local treatment of the keloid with triamcinolone as a standard of care therapy after consultation with the sponsor.

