#### **7.4.2.1 *Modified Vancouver Scar Scale***

The mVSS is a common tool for the assessment of keloid formation and will be used as the basis for defining keloid formation in this study. Scars observed at the biopsy wound sites will be evaluated and scored according to the mVSS (Fearnonti et al 2010, see [Appendix D](#)) at the time points outlined in [Appendix A](#), [Appendix B](#), and [Appendix C](#).

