### **8.2.4 Day 8**

- Complete DLQI.
- Obtain vital signs (blood pressure, heart rate, respiratory rate, and body temperature).

- Perform a brief, symptom-directed physical examination.
- Collect blood (predose) for the following:
  - Hematology;
  - Clinical chemistry.
- Collect urine (predose) for urinalysis.
- Perform physician assessment of keloid formation and volume.
- Assign mVSS and POSAS scoring ([Fearmonti et al 2010](#), see [Appendix D](#) and [Appendix E](#)).
- Administer intradermal study treatments.
- Review and record AEs and concomitant medications.
- Note: Biopsy wound sites are to be photographed at the time the investigator suspects a keloid may be forming, at the time of observation of an unconfirmed keloid, and at the time of keloid confirmation.

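### A single mVSS of 6 or more confirms a keloid with no earliest day, so a score taken while the wound is still being injected can count

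*Combined protocol and SAP*

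**What the plan says.** Section 3.2.2 opens with persistence: "The formation of a keloid will be defined as a persistent scar that exhibits a score of at least 3 on the mVSS", with a height score of at least 1. It then gives two routes to confirmation.

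- A scar scoring 3 to 5 is unconfirmed and "will be re-evaluated at the subsequent monthly visits for up to 12 weeks". It is confirmed only if it is still there afterwards.
- A scar that progresses to 6 or more "at any time (with a score of at least 1 in the height sub-domain) will be considered confirmed keloid(s".

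The Synopsis, Section 4.2 and Section 7.4.2 repeat the second route. None of them gives an earliest qualifying day, and neither does the analysis text in Section 11.4.4.

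The assessments start early. Section 7.4.2 states: "Excisional wound sites will be evaluated by the investigator for keloid formation (predose on dosing days"; Section 4.2 lists Days 8 and 12 among the assessment days. The visit lists order "Assign mVSS and POSAS scoring" on Day 8 and again on Day 12 in the 6-dose regimen (Sections 8.2.4 and 8.2.6), and on Days 8, 15 and 22 in the 12-dose regimen (Sections 8.4.4 and 8.4.5). All of these are dosing days.

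Confirmed keloid feeds the Week 24 proportion, the within-subject improvement proportion, the proportions "at 12 weeks, 36 weeks, 52 weeks, and at the time of study withdrawal", and the time to confirmed keloid (Sections 3.2.2 and 11.4.4). The exploratory mVSS endpoint in Section 3.2.4, by contrast, starts only at Day 29.

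**The concern.** One route tests persistence and the other does not. Appendix D rates colour, pliability and height on the day of the visit, so a single score cannot show that a scar persists. A wound sutured a week earlier and injected two or three days earlier may be red, firm and slightly raised for reasons unrelated to keloid formation.

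A reaction that later settles would still date the time to confirmed keloid. It would also remain in the proportions if status at a time point means confirmed at or before it. In the improvement endpoint the error can run either way: a false confirmation only at the placebo site creates an apparent success, and one only at the MRG-201 site hides a real one. With about 10 completers per cohort, a single such case is visible in the result.

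**Working it through.** **Step 1: the scale (Appendix D).** Vascularity runs 0 to 3, pliability 0 to 5 and height 0 to 3. The maximum is 3+5+3 = 11, which matches the stated total. There are 4×6×4 = 96 score combinations. Of these, 42 total at least 6 with height at least 1, and 10 of the 42 have the lowest raised height (under 2 mm). Two examples:

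- red 2 + firm 3 + under 2 mm 1 = 6
- red 2 + yielding 2 + 2–5 mm 2 = 6

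With normal pliability only 3+0+3 reaches 6. These counts show what the rule permits, not how often it happens.

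**Step 2: interval from the previous injection (dosing days in Section 6.2.1).**

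| Regimen | mVSS on dosing day | Previous injection | Interval (days) |
|---|---|---|---|
| 6-dose | 8 | 5 | 3 |
| 6-dose | 12 | 10 | 2 |
| 12-dose | 8 | 5 | 3 |
| 12-dose | 15 | 12 | 3 |
| 12-dose | 22 | 19 | 3 |

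**Step 3: earliest confirmation under each reading of progression.**

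- No earlier 3-to-5 score needed: Day 8.
- An earlier 3-to-5 score needed: Day 12 (from Day 8) in the 6-dose regimen, and Day 15 (from Day 8) in the 12-dose regimen.

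All of these fall in the dosing period.

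**Step 4: weight of one case.** Section 11.5 plans about 12 subjects to obtain about 10 at Week 24. One false confirmation moves a site proportion by 1/12 = 8.3% to 1/10 = 10%, that is, 8 to 10 percentage points.

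**Step 5: what a Day 29 start provides.**

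- 6-dose regimen (window ±3 days, last dose Day 12): 26−12 = 14 to 32−12 = 20 days after the last dose.
- 12-dose regimen (window ±1 day, last dose Day 26): 28−26 = 2 to 30−26 = 4 days after the last dose.
- Second cycle: its Day 29 visit is nominally 29−12 = 17 days after the last dose. A cycle started on Day 57 or Day 85 reaches it on 57+28 = Day 85 or 85+28 = Day 113. Retreated and untreated sites therefore stay on the same 4-weekly visits.

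A Day 29 start clears the dosing period well in the 6-dose regimen but only just in the 12-dose regimen.

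**The case against.** The strongest reply is textual. Section 3.2.2 speaks of progression directly after describing scars under observation, so the 6-or-more route may apply only to a scar already scored 3 to 5. The wording in Section 4.2, "If the wound site scar(s) progress to an mVSS score of 3 to 5", needs no earlier score, but it sits in the second-cycle paragraph and is weak evidence about a first-cycle Day 8 score. This stands as a point of interpretation. It does not remove the problem, because Step 3 shows that both scores can be obtained during dosing.

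Other points have some force:

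- Section 7.4.2.1 limits the scale to scars: "Scars observed at the biopsy wound sites will be evaluated and scored according to the mVSS". An investigator might decline to call a fresh wound a scar, but the visit lists order the score without that condition.
- The Appendix A row for physician keloid assessment starts at Day 19. Its mVSS row starts at Day 8, however, and Sections 4.2, 8.2.4 and 8.2.6 place the keloid assessment on Days 8 and 12.
- Redness and slight swelling alone do not reach 6. Section 2.3.1 describes Phase 1 injection-site reactions as mild or moderate, short, and not worse with repeat dosing. The frequency may therefore be low.
- The two-tier rule may be deliberate, with 6 of 11 taken as severe enough. But severity on one day is not persistence, which is the plan's own definition.
- Sides are randomised and blinded, both follow one rule, and photographs and volumes are collected. A transient score would be visible, but it would still be counted.
- Section 11.1 promises a more detailed SAP before any data review. It is not included here and may settle the matter.

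**Conclusion.** The point holds as a should-fix item. As written, the rule lets a score taken during dosing confirm a keloid under either reading of progression. The consequence is one-sided or two-sided misclassification in descriptive summaries, at 8 to 10 percentage points per case and site. Section 11.2 states that no formal hypothesis is tested, so no error rate or power is affected.

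Four stronger conclusions that a reader might infer are not supported:

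- **That early false confirmations are common, or dilute the treatment contrast by a known amount.** The documents give no frequency of early scores of 6 or more.
- **That the error works against MRG-201.** Section 2.3.1 reports injection-site edema or erythema in about one-third of Phase 1 subjects, but gives no mVSS scores and calls the reactions short. Neither the direction nor the size can be derived.
- **That the Week 24 proportion is necessarily affected.** This requires cumulative status. If status means the scar's condition at that visit, a regressed early score adds nothing.
- **That the Week 12 proportion rests almost wholly on the 6-or-more route.** This holds only if the 12-week observation period runs from the first 3-to-5 score (8+84 = Day 92, the last day of the Day 85 window). The text does not anchor that period.

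**What to change.** For endpoint classification only, by the same rule for both sites and with no change to clinical management, amend Section 3.2.2 and carry the rule into the SAP:

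- For the pharmacodynamic proportions and the time to confirmed keloid, the 6-or-more route uses only scores from the scheduled Day 29 visit and the following 4-weekly visits. First-cycle scores before Day 29 and second-cycle Day 8, 12 and 19 scores do not confirm by this route.
- The 3-to-5 route is unchanged, since its 12-week persistence requirement already screens out transient scores. An early score of 6 or more counts there as a score of at least 3.
- Sensitivity analyses: (a) the rule as now written, with the SAP stating how it reads progression and whether status is cumulative; (b) 6 or more at two consecutive 4-weekly visits; (c) in the 12-dose regimen, a start at Day 57, because Day 29 is only 2 to 4 days after the last dose.

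The cost is wording; no visit or assessment is added, and Day 29 is the start that Section 3.2.4 already uses. A few true early keloids would be dated to Day 29 or later. A subject who leaves before Day 29 has no classifiable status by this route and should be shown as such, not as keloid-free.

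Two contradictions need separate reconciliation by the sponsor. Appendix A starts the physician keloid assessment at Day 19, while Sections 4.2, 8.2.4 and 8.2.6 start it at Day 8. Section 3.2.2 allows local triamcinolone at confirmation, which can come early, while Section 6.3 does not permit local corticosteroids in the first 12 weeks.

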### **3.2.3 Other Pharmacodynamic Endpoints**

- Proportion of subjects forming confirmed keloids regardless of treatment application.
- Time to keloid formation.
- Volume of keloid at 24 weeks, 52 weeks and at time of triamcinolone injection (if applicable).

### **3.2.4 Exploratory Endpoints**

- Modified Vancouver Scar Scale (mVSS; [Fearmonti et al 2010](#), see [Appendix D](#)) score at visits occurring every 4 weeks from Day 29 to Day 365 after excisional wound creation.
- Patient and Observer Scar Assessment Scale (POSAS; [Appendix E](#)) scores at visits occurring every 4 weeks from Day 29 to Day 365 after excisional wound creation.
- Keloid volume and keloid severity (per mVSS in [Appendix D](#) and POSAS in [Appendix E](#)) at visits occurring every 4 weeks following a second cycle of dosing with MRG-201 or placebo in subjects exhibiting evidence that a keloid may be forming at one or both biopsy sites within 12 weeks after initiation of the first cycle of study dosing.

### 3.2.5 Pharmacokinetic Endpoints

- Plasma concentration of MRG-201 will be assessed at multiple time points on Day 1 and Day 12 (or Day 26 for cohorts dosing for 4 weeks), and at single time points on Day 2 and Day 13 (or Day 27 for cohorts dosing for 4 weeks). Voided urine samples for PK analyses will also be collected on Day 1 and 12 (or Day 26 for cohorts dosing for 4 weeks) predose and 3 hours postdose, and Day 2 and Day 13 (or day 27 for cohorts dosing for 4 weeks).

## 4 STUDY DESIGN

This is a double-blind, placebo-controlled, multi-center, outpatient exploratory efficacy study in subjects with a high likelihood of keloid formation (i.e., history of  $\geq 10$  keloids or history of large keloids,  $\geq 4$  cm), with MRG-201 and placebo administered by intradermal injection around the site of two separate punch biopsies.

A minimum of 12 subjects are anticipated for enrollment in the first cohort of the study to attain at least 10 subjects who complete study participation through 24 weeks after excisional wound creation. Subjects who drop out for reasons other than safety or study treatment tolerability may be replaced with sponsor approval (up to 16 total including replacements). The sponsor may enroll up to 5 additional cohorts of 12 to 16 subjects each (up to 80 total additional subjects) to assess lower doses and/or regimens.

Subjects in the initial cohort will undergo a screening period lasting up to 28 days, followed by a double-blind, 12-day active treatment period (first cycle of study dosing) conducted in the outpatient setting, a possible second 12-day cycle of study dosing as outlined in [Section 4.2](#), and a follow-up period of up to 52 weeks ( $\pm 7$  days) after initiation of the first cycle of study dosing. Subjects in additional cohorts may receive lower doses or an extended 26-day active treatment period without the option to receive a second cycle of treatment. Follow-up periods for those additional cohorts will remain unchanged.

Subjects will be continuously monitored for safety through evaluations of AEs, vital signs, physical examination findings, clinical laboratory measurements, and ECG monitoring.

Samples will be collected for plasma PK on Days 1, 2, 12, and 13 (or Days 1, 2, 26, and 27 for subjects receiving an initial 26-day treatment cycle).

The punch biopsy wound sites will be evaluated for keloid formation, photographic assessment, and clinical response during the active treatment and follow-up periods of the study. Biopsy

samples will be saved for future protein and/or nucleic acid analysis to assess MRG-201 effects in subjects who form keloids.

#### **4.1 Punch Biopsies**

On Day 1 of the study, subjects will be seen at the clinic in the morning to confirm study eligibility and for their baseline assessments, punch biopsy procedures, baseline photography of the biopsy sites, and administration of study treatments. Subjects will undergo two 6-mm punch biopsies bilaterally in the upper back/shoulder region in areas that can be covered with clothing and are likely to form keloids. The locations for the biopsies must be at least 10 cm from each other and far enough away from existing keloids that new keloid formation may be assessed. The punch biopsy excisional wound sites will be closed with sutures.

#### **4.2 Treatments Administered**

Following completion of the punch biopsies on Day 1, one punch biopsy wound site will be treated with MRG-201 and the other wound site will be treated with placebo. The treatment for each wound site will be randomized (left versus right) and blinded but consistent throughout dosing. MRG-201 and placebo will each be administered as four 20- $\mu$ L injections around one wound site, with subjects receiving approximately 5.3 mg of the MRG-201 active moiety on each dosing day (approximately 1.3 mg per 20- $\mu$ L injection). After all Day 1 assessments and procedures are complete, subjects will be discharged to home.

Subjects will return to the clinic on Days 3, 5, 8, 10, and 12 to receive repeat injections with the same blinded study treatment that was administered at each wound site on Day 1. Subjects will return to the clinic on Day 19 for additional assessments and safety monitoring, and the Principal Investigator (PI) will determine whether any tolerability concerns are present and warrant consultation and safety data review with the sponsor's Medical Monitor. If at any point clinically significant safety or tolerability issues are observed by the investigator and are thought to be possibly related or related to MRG-201, the subject will not receive further administration of MRG-201 pending follow-up with the Medical Monitor. In this event, the investigator must notify the sponsor's Medical Monitor by email or phone within 24 hours, and a meeting with the sponsor Medical Monitor may be convened.

On Day 8, Day 12, Day 19, Day 29 (4 weeks  $\pm$  3 days after completion of the punch biopsies) and then every 4 weeks for 1 year (Days 57, 85, 113, 141, 169, 197, 225, 253, 281, 309, 337, 365, each  $\pm$  7 days), excisional wound sites will be assessed for keloid formation, photographic evaluations, and other study assessments.

For subjects receiving 6 doses of MRG-201 in the initial treatment cycle, if there is evidence that a keloid may be forming (defined as meeting a score of 1 or 2 on the mVSS and having an appearance consistent with an area likely to form a keloid according to investigator judgement) within 12 weeks after initiation of the first cycle of study dosing, and following the initial 29-day treatment and assessment period, subjects will undergo a second cycle of study dosing in one or both biopsy sites (depending on keloid formation). Subjects will be treated with MRG-201 or placebo according to the original treatment assignments (blinding will be maintained during the second treatment regimen). The treatment regimen for the second cycle of study dosing will be the same as for the first cycle, i.e., an initial dose followed by additional doses 2, 4, 7, 9, and 11 days after the initial dose, with follow-up visits at Days 19 and 29 after the re-start of dosing. Following the visit that occurs 29 days after the start of the second cycle of study dosing, re-treated biopsy sites will be followed according to the first cycle visit schedule. If the wound site scar(s) progress to an mVSS score of 3 to 5 (with a score of at least 1 in the height sub-domain) after the 12-week observation period and/or to an mVSS score of  $\geq 6$  at any time (with a score of at least 1 in the height sub-domain), the scar(s) will be considered confirmed keloid(s). At the time of keloid confirmation, the investigator, in consultation with the subject, may elect to attempt local treatment of the keloid with triamcinolone as a standard of care therapy after consultation with the sponsor.

Additional cohorts may be enrolled to test lower doses or an extended dosing schedule. Study procedures for the extended dosing cohorts will be identical to the cohort described above, with the following exceptions: 1) subjects in these cohorts may receive a total of 12 intradermal doses of MRG-201 and placebo on Days 1, 3, 5, 8, 10, 12, 15, 17, 19, 22, 24, and 26; 2) subjects will not undergo a second cycle of treatment if the 4-week dosing schedule is used; and 3) pharmacokinetic assessments will be performed on study Day 1, 2, 26, and 27 for subjects receiving an initial 26-day treatment cycle.

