### **8.3 Second Cycle of Dosing with MRG-201 and/or Placebo**

For subjects receiving 6 doses of MRG-201 in the initial treatment cycle, if there is evidence that a keloid may be forming (defined as meeting a score of 1 or 2 on the mVSS and having an appearance consistent with an area likely to form a keloid according to investigator judgement) within 12 weeks after initiation of the first cycle of study dosing, and following the initial 29-day treatment and assessment period, subjects will undergo a second cycle of study dosing in one or both biopsy sites (depending on keloid formation). Subjects will complete the procedures that were planned at the scheduled visit (e.g., Day 85 visit procedures, if that is the current visit), as well as be treated with MRG-201 or placebo according to the originally assigned study treatments. The study assessments to be performed during the second cycle of study dosing are summarized in [Appendix B](#).

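### Keloid confirmation is worded in two conflicting ways: Section 3.2.2 requires a scar at mVSS 3–5 to persist for 12 weeks, while the re-dosing paragraph in Section 4.2 and the synopsis can be read as requiring no persistence

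*Combined protocol and SAP*

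**What the plan says.** Section 3.2.2 treats a scar at mVSS 3–5 with height at least 1 as unconfirmed. Such a scar "will be re-evaluated at the subsequent monthly visits for up to 12 weeks". It becomes a confirmed keloid by one of two routes: "Keloid(s) that persist after this 12-week observation period", or a score of 6 or more with height at least 1 at any time. Section 7.4.2 and the synopsis paragraph on endpoint assessment say the same. Section 3.2.2 covers either wound after the initial treatment and makes no exception for re-dosed sites.

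Section 4.2 allows a second 6-dose cycle in one or both wounds. The trigger is a score of 1 or 2 plus investigator judgement, within 12 weeks of the start of the first cycle. After stating that "re-treated biopsy sites will be followed according to the first cycle visit schedule", the paragraph continues: "If the wound site scar(s) progress to an mVSS score of 3 to 5" (height at least 1) "after the 12-week observation period and/or to an mVSS score of" 6 or more at any time, the scar is a confirmed keloid. The synopsis methodology section carries the same sentence. Neither place says which 12 weeks are meant, and neither mentions persistence.

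Confirmed keloid at 24 weeks, by product, is the leading pharmacodynamic endpoint (Sections 3.2.2 and 11.4.4). Improvement is also built on confirmed status: "no confirmed keloid formation in the treated lesion vs. confirmed keloid formation in the untreated lesion".

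**The concern.** The two wordings test different things. Section 3.2.2 asks whether a scar already at 3–5 is still there 12 weeks later. Section 4.2 asks whether a scar reaches 3–5 after some 12-week period. The second cannot literally refer to the Section 3.2.2 period, because that period starts only once the scar has reached 3–5. The only other 12-week span in the Section 4.2 paragraph runs from the start of the first cycle and ends at Day 85. An investigator could therefore confirm a scar at its first 3–5 score after Day 85.

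Two things are at stake. The first is the Week-24 classification, and with it time to confirmed keloid. The second is treatment: confirmation opens the option of triamcinolone. If a wound is confirmed early and injected, its later scores no longer show the untreated course, and a later derivation from the scores cannot restore it.

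**Working it through.** **Inputs.** Routine mVSS visits at Days 29, 57, 85, 113, 141, 169, 197, 225 and 253, with ±7 days from Day 57 on (Section 4.2). Week 24 is Day 169 (Section 7.4.3). The observation period is 12 weeks, or 84 days (Section 3.2.2). About 10 subjects per cohort are expected to complete 24 weeks (Section 11.5). A second cycle is taken to start at Day 29, 57 or 85; Section 8.3 itself gives the last of these as an example ("Day 85 visit procedures, if that is the current visit").

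**The plan's own day.** Week w falls on Day 1 + 7w. Week 24: 1 + 7 × 24 = 169, as stated. Week 12: 1 + 7 × 12 = 85. Week 36: 1 + 7 × 36 = 253.

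**Section 3.2.2, persistence route.** Confirmation day = first 3–5 day + 84, provided the scar persists.
- First score at Day 29, 57 or 85: 113, 141 or 169, in time for Week 24.
- First score at Day 113, 141 or 169: 197, 225 or 253, too late for Week 24.

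Visit windows do not rescue the later group. The earliest Day-113 visit is Day 106, and 106 + 84 = 190. The latest Week-24 visit is Day 169 + 7 = 176.

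**Section 4.2, by meaning of the 12 weeks.** The table gives the confirmation day for a scar that first scores 3–5 at the day shown and stays below 6. A dash means that the first 3–5 score falls before the period ends.

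| First 3–5 score | Section 3.2.2 period | From Day 1 (ends Day 85) | From re-start at Day 29 (ends 113) | From re-start at Day 57 (ends 141) | From re-start at Day 85 (ends 169) |
|---|---|---|---|---|---|
| Day 113 | 197 | 113 | 113* | – | – |
| Day 141 | 225 | 141 | 141 | 141* | – |
| Day 169 | 253 | 169 | 169 | 169 | 169* |

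*Only if a visit on the last day of the period counts as after it. The Section 3.2.2 column uses that same convention.

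Counted from Day 1, confirmation comes earlier by 197 − 113 = 225 − 141 = 253 − 169 = 84 days.

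**What does not change.** A score of 6 or more (height at least 1) confirms at once under both wordings. A scar that first scores 3–5 by Day 85 and stays there is a Week-24 keloid under Section 3.2.2. One that regresses need not be.

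**Size in one subject.** Suppose both wounds score 1–2 at Day 85 and 3 at Days 113, 141 and 169, and only the placebo wound was re-dosed. If Section 4.2 is counted from Day 1 and applied to the re-dosed wound alone, that wound is a keloid at Day 113. The MRG-201 wound cannot be one before Day 197, so the subject counts as improved at Week 24 on identical scores. One subject in 10 is 1/10 = 0.10, both on the placebo keloid proportion and on the improvement proportion. If the MRG-201 wound was the one re-dosed, its keloid proportion rises by 0.10. If Section 4.2 is applied to both wounds, both proportions rise by 0.10 and the difference does not move.

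The documents do not give the number of such subjects. Assuming 0 to 3 of 10, the shift is 0 to 0.30.

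**The case against.** The strongest reply is that Section 4.2 simply means the Section 3.2.2 period. The term for a 12-week observation period is the one Section 3.2.2 uses. Section 3.2.2 comes first, and nowhere else do the documents give that name to the 12 weeks from Day 1. On that reading the rules agree and only the verb is wrong. This is a plausible account of intent and limits how serious the point is. It does not remove the conflict: a scar cannot progress to 3–5 after a period that begins when it reaches 3–5, and in the synopsis the re-dosing sentence appears before the definition.

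A reader might go further and infer that the protocol sets one rule for re-dosed wounds and a stricter one for the others. The documents do not support that. The Section 4.2 sentence speaks of wound-site scars in general and is tied to re-dosing only by its position. Section 3.2.2 excepts no wound, and Section 7.4.2 places its definition over the visits in Appendix B, which is the second-cycle schedule. Nor is it true that a wound not re-dosed and first scoring 3–5 after Day 85 can never be a Week-24 keloid: it is one if it reaches 6 with height at least 1 by then.

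It can also be said that the SAP, due before unblinding or review of any data (Section 11.1), could derive status from the recorded scores, that triamcinolone is optional and needs sponsor consultation, and that no formal hypothesis is tested (Section 11.2). All of this holds. But Section 11.4.4 states no derivation rule, and derivation cannot undo an injection given early.

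**Conclusion.** The conflict in wording is real and touches the leading pharmacodynamic endpoint. Its effect depends on what the undefined 12 weeks mean: every scar first at 3–5 between Day 113 and Day 169 is reclassified at Week 24 if they run from Day 1, some are if they run from the re-start, and none are if they are the Section 3.2.2 weeks. Different treatment of a subject's two wounds is a possible misapplication, not something the protocol prescribes.

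The size is 0.10 per reclassified wound on that product's proportion with 10 completers, and up to 84 days in the timing of confirmation for a first score at a routine visit. These figures assume nominal visit days, scars that stay at 3–5, and a last-day visit counting as the end of the period. The number affected is unknown and may be zero. This is a wording correction worth making, of moderate priority.

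**What to change.** In Section 4.2 and the synopsis re-dosing paragraph, replace the sentence with: *Confirmation follows Section 3.2.2 for every wound, re-dosed or not; the 12 weeks run from that wound's first visit with mVSS 3 to 5 and height at least 1.* The Section 3.2.2 rule is the one to keep, since it already appears in three places. In Section 11.4.4 or the SAP, state that keloid status at each time point is derived from the recorded mVSS scores by this one rule.

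The cost is one sentence in two places and one sentence on derivation, with no new visits or data. If enrolment has begun, it needs an amendment or a clarification to sites. There are two downsides. Persistent scars that first score 3–5 after Day 85 and by Day 169 will appear at Week 36 (Day 253, already a listed time point) instead of Week 24. Their triamcinolone option will also come up to 84 days later than under the looser reading.
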